4.2 EXCLUSION CRITERIA

Patients must *not* meet any of the following criteria:

1. Prior history of any significant cardiac disease such as congestive heart failure, myocardial infarction, arrhythmia, or structural defects or suspicion thereof.
2. Leukopenia ($<3,000$ leukocytes/ μ L), neutropenia ($<1,500$ neutrophils/ μ L), or thrombocytopenia ($<125,000$ platelets/ μ L).
3. Low Hemoglobin (baseline hemoglobin below the lower limit of normal)
4. Prior history of anaphylaxis, angioedema or serious cutaneous drug reactions
5. Any sign of significant chronic active infection (e.g., hepatitis, tuberculosis, EBV, CMV, or toxoplasmosis), or screening laboratory evidence consistent with a significant chronic active infection (such as positive for HIV, PPD/IGRA, or HB_sAg). Significant acute infections must be resolved before treatment may commence, e.g., acute respiratory tract, urinary tract, or gastrointestinal tract infections.
6. Anticipated ongoing use of diabetes medications other than insulin that affect glucose homeostasis, such as metformin, sulfonylureas, thiazolidinediones, glucagon-like peptide 1 (GLP-1) mimetics, dipeptidyl peptidase IV (DPP-IV) inhibitors, or amylin.
7. Prior or current treatment that is known to cause a significant, ongoing change in the course of T1DM or immunologic status, including high-dose inhaled, extensive topical or systemic glucocorticoids.

8. Evidence of liver dysfunction, with alanine aminotransferase (ALT) or aspartate aminotransferase (AST) >2.0 times the upper limit of normal persistent for 1 week or greater.
9. Evidence of renal insufficiency as indicated by serum creatinine of >1.2 times the upper limit of normal confirmed in a repeat test at least 1 week apart.
10. Evidence of clinically significant metabolic bone disease (except adequately treated rickets).
11. Females who are pregnant at the time of screening, breastfeeding or unwilling to defer pregnancy during the 24-month study period. (Female participant must be at least 100 days postpartum before enrollment into study).
12. Prior treatment with imatinib or related tyrosine kinase inhibitor.
13. Unable to avoid medications that affect CYP3A4: either inducers that may decrease imatinib levels, or inhibitors that may increase drug concentrations. (Refer to section 1.5.1.12 for a complete list of inducers and inhibitors.)
14. Height standard deviation score ≥ 2 standard deviations below mean (participants of growing-age potential)
15. Any sign of QT prolongation on Visit -1 ECG (> 450 ms in males and > 470 ms in females).
16. Known coagulation disorders or use of anticoagulants
17. Current and anticipated on-going treatment with drugs that may increase or decrease imatinib plasma concentrations (CYP3A4 family inhibitors or inducers) or drugs that may have their plasma concentration altered by imatinib (drugs metabolized by CYP3A4/5 and CYP2D6).
18. Any condition that, in the investigator's opinion, may compromise study participation or may confound the interpretation of the study results.

4.3 PREMATURE TERMINATION OF A PARTICIPANT FROM THE STUDY

Prematurely terminated participants will be asked to remain in the study and participate in follow-up. If study treatment is discontinued, the medical monitor should be notified. Participants who prematurely terminate from the study will not be replaced.

Withdrawal of consent. Participants who withdraw consent will be asked to participate in follow-up. If the participant does not consent to follow-up visits, they should complete an end-of-study visit, which will include all the assessments listed for Visit 11 in Appendix 1.

Failure to return. Participants who do not return for visits and who do not respond to repeated attempts by the site staff to have them return will be considered *lost to follow-up*.

Investigator judgment. A severe or serious AE occurs, which, based on the medical judgment of the investigator, prevents completion of participation in the study.

5. STUDY MEDICATIONS

5.1 INVESTIGATIONAL MEDICATION

5.1.1 Formulation and Packaging

Imatinib mesylate (Gleevec; Novartis, East Hanover, NJ) is produced as film-coated tablets, equivalent to 100 mg of imatinib free base. The placebo group will receive an identical pill that is manufactured and distributed by a designated drug distributor. If necessary to prevent unblinding, the distributor may need to overencapsulate the imatinib tablets.

5.1.2 Dosage, Preparation, and Administration

Adult participants will receive four 100 mg tablets of imatinib or the corresponding placebo tablets daily for the first 6 months. Pediatric participants will receive 260 mg/m²/day (rounded up or to the closest 100 mg) or 400 mg/day (whichever is smaller) of active drug or placebo.

5.1.3 Recommended Storage Conditions

- Store at 25°C (77°F); excursions permitted to 15–30°C (59–86°F).
- Protect from moisture.
- Dispense in a tight container, USP.

5.2 DOSE MODIFICATION AND MANAGEMENT OF ADVERSE EVENTS

With the use of a relatively low dose of imatinib in an otherwise healthy population, we hope to minimize the nature and extent of AEs experienced. It is important to note here, as in section 1.4, that the AEs referenced below, if observed, will usually occur early in the course of treatment, are often self-limited, and do not usually require dose adjustment or discontinuation of imatinib. Nonetheless, the investigative team recognizes that cancer treatment is clearly different than the proposed elective clinical trial: side effects considered acceptable and tolerable in a cancer setting may not be considered in the same light for subjects in this study. Every effort will be made to carefully balance the intent to provide the maximum total prescribed dose of study drug to subjects, versus the discomfort and risk that may be accompanied with imatinib administration. The “art” of subject management in this study will be to minimize the number of subjects that drop out of the trial due to these side effects, working in close concert with the investigative team to either adjust study drug dose and/or provide symptomatic relief with concomitant medications. General guidelines are outlined below, but may need to be modified as deemed necessary, in consultation with the trial physicians and medical monitor. In general, when a dose reduction is required, the daily dose of imatinib or placebo will be halved: For adults, the dose will be reduced from

400 mg/day to 200 mg/day. Unless otherwise stated, the equivalent dose reduction in children will be from 260 mg/m²/day to 130 mg/m²/day. Investigators will be instructed to always round up to the nearest 50 mg increment for the half-dose dosage.

5.2.1 Gastrointestinal Reactions

Nausea. To minimize issues with nausea, participants will be advised to take study medication with the largest meal of the day. If the problem persists, they may need to split the study medication into twice daily dosing.

For recurrent, persistent vomiting, grades 1 and 2, lasting for 48 hours, investigators will consider the use of anti-emetics such as prochlorperazine or ondansetron. Subjects usually respond promptly, and dose reduction is seldom needed.

For grade 2 vomiting that persists for 48 hours despite the use of antiemetic drugs, imatinib will be reduced to 50% of the initial daily dose. If vomiting resolves over the ensuing week, then the full dose will be restored. If vomiting recurs, then the subject will need to remain on the 50% tolerated lower dose, and re-evaluated weekly, with return to full dose reconsidered.

For vomiting that is grade 3, or grade 2 that does not improve with anti-emetics and dose reduction for 48 hours,, imatinib will be suspended until the problem is resolved. Electrolytes should be obtained. Imatinib will then be reintroduced at 50% of the initial daily dose. If vomiting does not recur over the ensuing week, the initial dose will be restored. If vomiting of grade 3 recurs, then the drug will be permanently discontinued. If nausea or vomiting resolve and then occur again at a later time, the same procedures may be followed as outlined above, depending on the grade.

Diarrhea. If it occurs, diarrhea is often mild and requires no specific therapy. For persistent diarrhea (1 week or greater) of grades 1 and 2 the participant may be treated with antidiarrheal and antispasmodic drugs, such as Imodium®, Lomotil®, or paregoric, at the discretion of the investigator.

For grade 2 diarrhea that persists for 1 week despite the use of antidiarrheal drugs, imatinib will be reduced to 50% of the initial dose. If diarrhea improves to less than or equal to grade 1 for at least 1 week, the initial dose will be restored. If diarrhea persists despite use of antidiarrheal drugs and dose reduction, permanent discontinuation of imatinib will be considered.

For diarrhea of grade 3 or higher, imatinib will be suspended until the problem is resolved. Electrolytes should be obtained. Imatinib will then be reintroduced at 50% of the initial dose for 1 week. If diarrhea does not recur, the initial dose will be restored. If diarrhea greater than grade 2 recurs, imatinib will be permanently discontinued. If diarrhea resolves and then occurs again at a later time, the same procedure may be followed.

Chronic diarrhea, of 14 or more days in duration, should be evaluated to determine if there is an infectious cause. Evaluation will be conducted in consultation with local infectious disease consultants, and will include a thorough clinical and epidemiological evaluation, including travel history and any possible exposures. Stool culture and other evaluation may be required, and anti-microbial therapy offered as indicated. Other potential causes of diarrhea, such as lactase deficiency, should be considered.

5.2.2 Muscle Cramps, Bone Pain, Arthralgias

Mild to moderate cramps may respond to calcium and magnesium supplementation, and some have responded to quinine. Mild to moderate bone pain and arthralgia can usually be relieved with nonsteroidal anti-inflammatory drugs (NSAIDs) such as ibuprofen and naproxen.

For grade 2 muscle cramps, bone pain or arthralgia that persist for 1 week despite the use of symptom-relieving drugs, the dose of imatinib will be reduced to 50% of the initial daily dose. If symptoms improve to less than or equal to grade 1 for at least 1 week, the initial dose will be restored. If symptoms persist despite symptomatic treatment and dose reduction, permanent discontinuation of imatinib will be considered.

For grade 3 muscle cramps, bone pain or arthralgia, imatinib will be suspended until the problem is resolved. Imatinib will then be reintroduced at 50% of the initial dose for 1 week. If symptoms do not recur, the initial dose will be restored. If symptoms greater than grade 2 recur, imatinib will be permanently discontinued.

5.2.3 Edema

Edema associated with imatinib is usually mild and self-limited, and often does not require therapy. Affected participants may consider a reduction in salt intake. Patients with periorbital edema may benefit from topical 0.25% phenylephrine or 1% hydrocortisone.

Localized edema. Grade 2 localized edema, including periorbital edema and limb edema, that persists for longer than 1 week may be treated with diuretics. For grade 2 edema that persists despite the measures described above, the dose of imatinib will be reduced to 50% of the initial daily dose. If edema improves to less than or equal to grade 1 for at least 1 week, the initial dose will be restored. If edema persists despite reductions in salt intake, use of diuretics, and imatinib dose reduction, permanent discontinuation of imatinib will be considered.

For edema of grade 3 or higher, imatinib will be suspended until the problem is resolved. Imatinib will then be reintroduced, with ongoing diuretic use, at 50% of the initial daily dose for 1 week. If edema does not recur, the initial dose will be restored. If edema greater than grade 2 recurs, imatinib will be permanently discontinued. If localized edema resolves and then occurs again at a later time, the same procedure may be followed.

Generalized fluid retention. Participants will be monitored for signs and symptoms of generalized fluid retention (including pulmonary and cardiac issues), and will be weighed regularly at each study visit to detect the early onset of fluid retention. If sudden increases in weight occur, participants should be examined for signs of pulmonary edema, pleural effusion, pericardial effusion, and ascites. If any signs of generalized fluid retention are found, imatinib should be suspended and diuretic therapy started. Electrolytes should also be obtained if greater than grade 2. If these measures lead to a prompt resolution of fluid retention, imatinib may be reintroduced at 50% of the initial daily dose. If fluid retention does not recur, the initial dose may be restored. If generalized fluid retention recurs, imatinib will be permanently discontinued.

5.2.4 Cutaneous Reactions

Rash. Investigators should be prepared for rashes early in the course of therapy, when they are most likely to occur. These are usually grades 1 or 2 and are self-limited. Symptomatic treatment with antihistamines, salves, and coal tar preparations has been helpful.

For grade 2 rash that persists for 1 week despite the measures described above, the dose of imatinib will be reduced to 50% of the initial daily dose. If the rash improves to less than or equal to grade 1 for at least 1 week, the initial dose will be restored. If the grade 2 rash persists despite symptomatic treatment and imatinib dose reduction, permanent discontinuation of imatinib will be considered. If grade 2 rash resolves and then occurs again at a later time, the same procedure may be followed.

For a rash of grade 3 or higher, imatinib will be suspended until the problem is resolved. Imatinib will then be reintroduced at 50% of the initial dose for 1 week. If the rash does not recur, the initial dose will be restored. If a rash greater than grade 2 recurs, imatinib will be permanently discontinued.

Bullous dermatologic reactions. Rare cases of bullous dermatologic reactions, including erythema multiforme and Stevens-Johnson syndrome, have been reported with imatinib treatment.

In cases of less than or equal to grade 1 erythema multiforme, imatinib will be suspended. If the condition resolves promptly, reintroduction of imatinib may be considered, starting at the lowest dose (100 mg/day) with gradual dose escalation, if tolerated. If the condition recurs at any grade, imatinib will be permanently discontinued.

If a participant presents with Stevens-Johnson syndrome (any grade), toxic epidermal necrolysis (any grade), or > grade 1 erythema multiforme, imatinib will be permanently discontinued and supportive therapy, including systemic glucocorticoids, started immediately.

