5.3 DISCONTINUATION OF STUDY MEDICATION IN AN INDIVIDUAL PARTICIPANT

Study medication according to study specifications will be discontinued for an individual participant if *any* of the following occurs:

- A discontinuation criterion for imatinib, as noted in section 5.2, is met.
- Clinical evidence of cardiac toxicity, such as congestive heart failure or significant cardiac arrhythmias, is observed.
- Pregnancy occurs.
- A severe or serious AE occurs, which, based on the medical judgment of the investigator, prevents a participant from completing the study treatment (see section 8 for classification of AEs).
- The investigator determines that it is in the participant's best interest to discontinue treatment.
- The participant, or participant's legal representative, requests that treatment be halted.

Further care will be provided according to the judgment and practice of the investigator.

The participant will be asked to remain in the study and participate in follow-up. If study treatment is discontinued, the medical monitor should be notified.

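### Section 5.2.4 re-challenges by default after any non-bullous rash of grade 3 or higher, with no automatic stop for a first grade 4 or severe exfoliative rash

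*Combined protocol and SAP*

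**What the plan says.** Section 5.2.4 handles skin reactions under two labels.

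**Rash.** From grade 3 upward the text reads "For a rash of grade 3 or higher, imatinib will be suspended until the problem is resolved. Imatinib will then be reintroduced at 50" percent of the initial dose, for one week. Without recurrence, the initial dose is restored. The permanent stop is tied to recurrence of a rash above grade 2, not to the first event.

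**Bullous reactions.** After erythema multiforme of grade 1 or less that resolves promptly, "reintroduction of imatinib may be considered, starting at the lowest dose (100 mg/day) with gradual dose escalation, if tolerated". On recurrence the rule is strict: "If the condition recurs at any grade, imatinib will be permanently discontinued". A permanent stop at the first event is written for Stevens-Johnson syndrome and toxic epidermal necrolysis at any grade, and for "> grade 1 erythema multiforme, imatinib will be permanently discontinued and supportive therapy, including systemic glucocorticoids, started immediately".

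Three general provisions bear on this. Section 5.2 sets the adult half dose ("400 mg/day to 200 mg/day") and says of its own rules: "General guidelines are outlined below, but may need to be modified as deemed necessary, in consultation with the trial physicians and medical monitor". Section 5.3 stops study drug when "A discontinuation criterion for imatinib, as noted in section 5.2, is met". It also does so for a severe or serious event that the investigator judges to prevent completion of treatment, or when the investigator considers stopping to be in the participant's best interest. Section 8.2 sends serious adverse events to the Coordinating Center within 24 hours and on to safety review.

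**The concern.** The rash rule has a floor (grade 3) and no ceiling. Read as written, a participant whose first rash was life-threatening is put back on the drug once it resolves, and is on full dose a week later. Severe exfoliative rash is a known imatinib risk in section 1.5.1.4, but section 5.2.4 does not name it. Unless it is classed with the bullous reactions, it follows the same path when it is grade 3 or higher.

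The trial is elective and not in cancer, and section 5.2 itself says that side effects acceptable in oncology may be viewed differently here. At stake is the safety of one or perhaps no participant. The primary analysis, sample size and endpoint are untouched.

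**Working it through.** The plan states no figure on this point, so there is none to reproduce. The check sets the two rules side by side, looks for text elsewhere that closes the gap, and then sizes the event.

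**1. The two restart rules in section 5.2.4 (adult dose; section 9.4 says only adults are enrolled at this time)**

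| | Non-bullous rash, grade 3 or higher | Erythema multiforme, grade 1 or less |
|---|---|---|
| Restart | Stated as what will happen | Optional |
| Precondition | Resolution | Prompt resolution |
| Starting dose | 0.5 × 400 = 200 mg/day | 100 mg/day |
| Return to 400 mg/day | After 1 clean week | Gradual, step length not given |
| Permanent stop | Recurrence above grade 2 | Recurrence at any grade |

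The starting doses differ by 200 / 100 = 2. Which schedule reaches full dose first cannot be determined. With assumed steps of 2 to 14 days, three 100 mg steps take 6 to 42 days and two doublings take 4 to 28 days, against 7 days for rash.

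**2. Is a first grade 4 or exfoliative rash stopped elsewhere?**

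- Section 5.2.4, permanent-stop sentence: only the three named bullous reactions.
- Section 5.3, first bullet: carries whatever section 5.2 requires, so it adds nothing where 5.2.4 requires no stop.
- Section 5.3, severe or serious event and best-interest bullets: real stop routes, both resting on judgment.
- Section 5.2: rules may be modified in consultation, again on judgment.
- Sections 3.7.1 and 8.2: review by the medical monitor, Safety Monitoring Committee and DSMB, with no stated dosing consequence for the individual.

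**3. How often might it arise?**

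Inputs: p = 1/500 for severe exfoliative rash (section 1.5.1.4, oncology experience); n = 44 on imatinib (66 × 2/3), or 46 as printed in section 9.4. Formula: P(at least one) = 1 − (1 − p)^n.

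| p | n = 44 | n = 46 |
|---|---|---|
| 1/500 | expected 0.088; 8.4% | expected 0.092; 8.8% |
| 1/1000 (assumed) | 4.3% | 4.5% |
| 1/2000 (assumed) | 2.2% | 2.3% |

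The lower rates are assumptions, included because the protocol expects milder and rarer side effects in this younger, healthier population. All rows are upper figures for the gap, since some exfoliative rashes may be classed as bullous reactions that already stop.

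No grade 4 figure can be derived. Section 1.5.1.4 puts higher-grade rash at about 3%, without saying whether of patients or of rashes and without separating grade 3 from grade 4.

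**4. Effect of an extra permanent stop on section 3.7.2 (taking treated to mean on imatinib, n = 44)**

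- One stop: 1/44 = 2.3%.
- The 20% limit: 0.20 × 44 = 8.8, so 9 participants.
- Two of the first 10: the chance of even one severe exfoliative rash among 10 is 1 − (499/500)^10 = 2.0%.

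**The case against.** The strongest reply is that the protocol already has safeguards. The section 5.2 rules are expressly flexible, and section 5.3 offers two routes to stop. A life-threatening rash is a serious adverse event under section 8.1.2 and so comes to central review; the medical monitor, trial physician or chairs can also refer it to the DSMB under section 3.7.1. This stands, and it lowers the priority. It does not close the gap, because each route needs someone to depart from a rule that says the drug will be restarted. For the bullous reactions the protocol wrote an automatic stop instead of relying on discretion.

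Three stronger readings are tempting and are not supported.

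- A reader might infer that a grade 4 rash is restarted faster than mild erythema multiforme. Both restarts wait for resolution, nothing shows a shorter time to the first re-dose for rash, and the escalation step for erythema multiforme is not given. What is established is the higher starting dose, the firmer wording and the looser recurrence threshold.
- A reader might infer that severity has been inverted. Erythema multiforme is grouped with the bullous reactions, so stricter handling of a mild case is also a choice by reaction type. The contrast shows that the section can be more cautious; it does not show an error.
- A reader might infer a contradiction with exclusion 4 ("Prior history of anaphylaxis, angioedema or serious cutaneous drug reactions"). Entry bars are not stopping thresholds in this protocol. Section 4.2 excludes neutrophils below 1,500 and persistent transaminases above 2 times the upper limit. Sections 5.2.5 and 5.2.6 nevertheless restart drug after on-study neutrophils below 1,500 or transaminases above 3 times the limit.

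It is also fair to say that diarrhea and localized edema share the open wording from grade 3 upward. This point is confined to rash.

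**Conclusion.** The point holds as a gap in a safety rule. For a first non-bullous grade 4 rash, or a severe exfoliative rash of grade 3 or higher outside the three named bullous reactions, the written default is re-challenge and no stop is automatic. Its size is small: at most about an 8.4% chance of at least one severe exfoliative rash among 44 on imatinib, falling to about 2% if the rate is a quarter of the oncology figure. This rests on the quoted 1 in 500 and on a 2:1 split of 66. The grade 4 part rests on the section 8.1.4 scale alone, with no rate available. Priority is low to modest; the edit is worth making because it is cheap.

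**What to change.** In section 5.2.4:

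1. Limit the reintroduction rule to *a grade 3 rash*.
2. Add a separate sentence: *Imatinib will be permanently discontinued for a grade 4 rash, or a grade 3 or higher rash that the investigator describes as exfoliative, unless the event is judged Unrelated or Unlikely related (8.1.5).*

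The new sentence should take precedence over the grade 3 rule. Keeping it separate leaves the immediate systemic glucocorticoid instruction with the bullous list only. Tying exfoliative to the investigator's description avoids an undefined category. Both attribution codes need naming, because section 8.1.5 lists Unlikely among the related categories. A grade 4 rash exempted in this way would be left to judgment under section 5.3. Making reintroduction after grade 3 rash optional is a further choice, not a necessary one. Section 5.3 needs no edit, since its first bullet picks up the new criterion.

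The cost is one edited sentence, one new sentence and a rare extra permanent stop, which counts toward section 3.7.2 if drug-related. Section 5.3 asks such participants to stay in follow-up, so the week 52 C-peptide need not be lost. Sample size and analysis do not change.
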